8. SCREENING VISIT AND STUDY VISITS 1-4

- Site screening visit
- Data to be recorded:

General parameters:

Initials

Date of birth

Sex

Smoker (yes/no/ex-smoker)

Race (NIH categories)

Ethnicity (NIH categories)

Case history

Date of confirmation of the diagnosis

Classification of UC before IPAA (proctitis, left sided colitis, pancolitis)

Type of extraintestinal symptoms

Specific therapies for pouchitis within the last year

Type of medication

Specific therapies for pouchitis within the last 4 weeks

Type of medication

Examinations

Vital signs: blood pressure (mm Hg), heart rate (min⁻¹), weight (kg), calculation of BMI, temperature

Height (cm)

Physical examination:

- Head (including ENT and eyes)
- Lymphatic system
- Endocrine system
- Lungs and respiratory tract
- Peripheral vascular system
- Cardiovascular system

- Gastrointestinal tract, liver, spleen
- Urogenital system
- Nervous system
- Muscular and skeletal system
- Skin and connective tissue
- Other

each: actual status: Present finding / normal condition / not examined

Blood sampling and measurement of laboratory parameters

- Hematology
- Serum chemistry
- Urine pregnancy test
- Stool sample for C. difficile toxin

Formal aspects:

Informed consent procedure

Verification of inclusion / exclusion criteria (eligibility check), as far as possible

Dispense stool collection kit for stool sample (stool sample should be brought back at visit week 0)

Explain and distribute stool diary to study patient

Perform test if patient is able to swallow an empty FMT test capsule

• Visit 1: Site visit week 0

Examinations

Vital signs: blood pressure (mm Hg), heart rate (min-1), weight (kg), temperature

Physical examination:

- Head (including ENT and eyes)	- Gastrointestinal tract, liver, spleen
- Lymphatic system	- Urogenital system
- Endocrine system	- Nervous system
- Lungs and respiratory tract	- Muscular and skeletal system
- Peripheral vascular system	- Skin and connective tissue
- Cardiovascular system	- Other

each: actual status: Present finding / normal condition / not examined

Blood sampling and measurement of laboratory parameters (must be performed in the 24 hours before *FMT*)

- Urine pregnancy test

Dispense stool collection kit for stool sample (stool sample should be brought back at visit week 2)

Formal Aspects:

Calculation of the mPDAI

Verification of inclusion / exclusion criteria (eligibility check)

Randomization

Dispense oral FMT or placebo Dispense omeprazole 20 mg (1 tablet) daily for 14 days during oral FMT Dispense PDAI diary Dispense adverse events diary

Pouchoscopy: Evaluation of endoscopic PDAI and perform "blinded" (real or placebo) FMT.

• Visit 2: Phone visit week 1 (7 (+1 day) days after endoscopic FMT /placebo and on oral FMT/placebo)

Formal aspects:

Adverse events (review adverse events diary)

Concomitant medication

Calculation of clinical mPDAI (stool frequency, rectal bleeding, fecal urgency/abdominal cramping, fever)

• Visit 3: Site visit week 2 (15 +3 days after endoscopic FMT /placebo and on oral FMT/placebo)

Formal aspects:

Adverse events (review adverse events diary)

Concomitant medication

Calculation of clinical mPDAI (stool frequency, rectal bleeding, fecal urgency/abdominal cramping, fever)

Reminder stool collection on day 15, 16 or 17 (day 1-3 after end of oral FMT) and bring in stool.

• Visit 4: Phone visit week 4 (2-3 days before planned week 4 site visit)

Formal aspects:

Adverse events (review adverse events diary)

Concomitant medication

Reminder to bring stool day 25, 26 or 27.

Calculation of clinical mPDAI (stool frequency, rectal bleeding, fecal urgency/abdominal cramping, fever)

If patient is in clinical remission (mPDAI ≤ 4) and no need for antibiotics plan for pouchoscopy week 4

If patient is not in clinical remission (mPDAI > 4) or need for antibiotics or comes in due to exacerbation of symptoms with possibility to continue with open label extension. Need to restart 10 day course of antibiotics as standard of care similar to initial antibiotic treatment before the first FMT

• Visit 5: Site visit Week 4 (day 28 +/- 3 days after first transplant) or early termination visit due to flare (day 1-28 after first transplant)

Examinations

Vital signs: blood pressure (mm Hg), heart rate (min-1), weight (kg), temperature

Physical examination:

- Head (including ENT and eyes)
 Lymphatic system
 Endocrine system
 Lungs and respiratory tract
 Peripheral vascular system
 Skin and connective tissue
- Cardiovascular system

- Other

each: actual status: Present finding / normal condition / not examined

Measurement of laboratory parameters

Hematology Serum chemistry

Stool collection: Bring to visit.

Formal aspects:

Return of study medication (empty containers)

Compliance assessment (count of empty containers returned)

Concomitant medication

Adverse events (review adverse events diary)

Calculation of mPDAI score (before pouchoscopy)

Pouchoscopy (in patients in clinical remission and no need for antibiotics only): Evaluation of endoscopic PDAI.

If patient is in clinical remission (mPDAI ≤ 4) and no need for antibiotics proceed to pouchoscopy

If patient is not in clinical remission (mPDAI > 4) or need for antibiotics or comes in due to exacerbation of symptoms with possibility to continue with open label extension. Need to restart 10 day course of antibiotics as standard of care similar to initial antibiotic treatment before the first FMT

In case of **premature withdrawal** from the study (yes, no)

If yes, reason:

- Intolerance of medication
- Lack of efficacy (need for steroids e.g. increase of steroids or re-introduction of steroids after previously successful taper)
- Severe adverse event
- Lack of patient's cooperation
- Inclusion criterion not fulfilled or exclusion criterion fulfilled coming to knowledge after recruitment
- Other reason

9. FOLLOW-UP VISITS OF PATIENTS IN REMISSION AT WEEK 4 OR NOT PARTICPATING IN THE OPEN LABEL EXTENSION

• Visit 6: Phone visit week 6 (42 +/- 3 days after first transplant)

Formal aspects:

Adverse events (review adverse events diary, last day of filling out the diary is 28 days after end of oral FMT, which is around week 6; patient needs to be advised to bring filled out diaries to visit 7)

Concomitant medication

Calculation of clinical mPDAI (stool frequency, rectal bleeding, fecal urgency/abdominal cramping, fever)

• Visit 7: Site visit week 8 (56 +/- 5 days after first transplant)

Examinations

Vital signs: blood pressure (mm Hg), heart rate (min-1), weight (kg), temperature

Physical examination:

- Head (including ENT and eyes)
- Lymphatic system
- Endocrine system
- Lungs and respiratory tract
- Peripheral vascular system
- Cardiovascular system

- Gastrointestinal tract, liver, spleen
- Urogenital system
- Nervous system
- Muscular and skeletal system
- Skin and connective tissue
- Other

each: actual status: Present finding / normal condition / not examined

Measurement of laboratory parameters

Hematology Serum chemistry

Stool collection: Bring to clinic.

Formal aspects:

Concomitant medication

Adverse events (adverse events diary filled out until visit 6)

Calculation of mPDAI score

Reminder stool collection and bring in stool week 16.

Collect adverse event diary (filled out until week 6)

• Visit 8: Site visit week 16 (112 +/- 7 days after first transplant)

Formal aspects:

Adverse events

Concomitant medication

Calculation of clinical mPDAI (stool frequency, rectal bleeding, fecal urgency/abdominal cramping, fever)

Stool collection: Stool collection

• Visit 9: Phone visit week 24 (168 +/- 10 days after first transplant)

Formal aspects:

Review if serious adverse events occurred in previous 8 weeks

10. FOLLOW UP VISITS OF PATIENTS PARTICIPATING IN OPEN LABEL EXTENSION AFTER WEEK 4

• Visit 6OL: Site visit week 6 (week 0 OL)

This visit should be performed after the patient completed at least 10 days of antibiotics

Examinations

Vital signs: blood pressure (mm Hg), heart rate (min-1), weight (kg)

Physical examination:

- Head (including ENT and eyes)
- Lymphatic system
- Endocrine system
- Lungs and respiratory tract
- Peripheral vascular system
- Cardiovascular system

- Gastrointestinal tract, liver, spleen
- Urogenital system
- Nervous system
- Muscular and skeletal system
- Skin and connective tissue
- Other

each: actual status: Present finding / normal condition / not examined

Formal aspects:

Concomitant medication Calculation of mPDAI score (before pouchoscopy) Dispense oral FMT capsules Dispense omeprazole 20 mg (1 tablet) daily for 14 days during oral FMT Dispense PDAI diary Dispense adverse events diary for OL follow-up phase

Blood sampling and measurement of laboratory parameters (be performed in the 24 hours before FMT)

- Urine pregnancy test

Pouchoscopy: Evaluation of endoscopic PDAI and perform FMT.

• Visit 7OL: Phone visit week 7 (week 1 OL; 7 days (+1 day) after second transplant)

Formal aspects:

Adverse events (review adverse events diary)

Concomitant medication

Calculation of clinical mPDAI (stool frequency, rectal bleeding, fecal urgency/abdominal cramping, fever)

• Visit 8OL: Site visit week 8 (week 2 OL, 15 + 3 days after second transplant)

Formal aspects:

Adverse events (review adverse events diary)

Concomitant medication

Calculation of clinical mPDAI (stool frequency, rectal bleeding, fecal urgency/abdominal cramping, fever)

Reminder stool collection on day 15, 16 or 17 (day 1-3 after end of oral FMT) and bring in stool. Plan for pouchoscopy visit 9OL

• Visit 9OL: Site visit week 10 (week 4 OL, 28 +/- 3 days after second transplant)

Examinations

Vital signs: blood pressure (mm Hg), heart rate (min-1), weight (kg)

Physical examination:

- Head (including ENT and eyes)
- Lymphatic system
- Endocrine system
- Lungs and respiratory tract
- Peripheral vascular system
- Cardiovascular system

- Gastrointestinal tract, liver, spleen
- Urogenital system
- Nervous system
- Muscular and skeletal system
- Skin and connective tissue
- Other

each: actual status: Present finding / normal condition / not examined

Measurement of laboratory parameters

Hematology Serum chemistry

Stool collection: Bring in.

Formal aspects:

Concomitant medication

Adverse events (review adverse events diary) Calculation of mPDAI score Pouchoscopy: Evaluation of endoscopic PDAI.

• Visit 10OL: Phone visit week 12 (week 6 OL; 42 +/- 3 days after second transplant)

Formal aspects:

Adverse events (review adverse events diary, which needs to be filled out 28 days after the last FMT, which is week 6 OL)

Concomitant medication

Calculation of clinical mPDAI (stool frequency, rectal bleeding, fecal urgency/abdominal cramping, fever)

• Visit 11OL: Site visit week 14 (week 8 OL; 56 +/- 5 days after second transplant)

Examinations

Vital signs: blood pressure (mm Hg), heart rate (min-1), weight (kg)

Physical examination:

- Head (including ENT and eyes)
- Lymphatic system
- Endocrine system
- Lungs and respiratory tract
- Peripheral vascular system
- Cardiovascular system

- Gastrointestinal tract, liver, spleen
- Urogenital system
- Nervous system
- Muscular and skeletal system
- Skin and connective tissue
- Other

each: actual status: Present finding / normal condition / not examined

Measurement of laboratory parameters

Hematology Serum chemistry

Stool collection: Bring in.

Formal aspects:

Concomitant medication

Adverse events

Calculation of mPDAI score Reminder for stool collection week 16

Collect adverse event diary (filled out until week 60L)

• Visit 12OL: Site visit week 22 (week 16 OL; 112 +/- 5 days after second transplant) Formal aspects:

Adverse events

Concomitant medication

Calculation of clinical mPDAI (stool frequency, rectal bleeding, fecal urgency/abdominal cramping, fever)

Stool collection: Stool collection

• Visit 13OL: Phone visits week 30 (week 24OL 168 +/- 10 days after second transplant)

Formal aspects:

Review if serious adverse events occurred in previous 8 weeks

11. POUCHOSCOPY AND LABORATORY PARAMETERS

• Pouchoscopy (Screening, visit 5 or visit 6OL)

Pouchoscopy will be performed to evaluate the pouch, prepouch ileal segment and the cuff. The pouch and prepouch inflammation will be graded according mPDAI (see attachment).

• Laboratory parameters

All laboratory analyses will be carried out in at the local laboratory of the investigational site.

Acute phase reactants (nonspecific inflammatory markers)

C-reactive protein (CRP)

Hematology:

Blood count (erythrocytes, hemoglobin, hematocrit, leukocytes, platelets)

Serum chemistry:

Kidney function: creatinine

Liver function (alanine aminotransferase {ALT}, aspartate aminotransferase {AST}, alkaline phosphatase, bilirubin)

Urine pregnancy test screening visit and in the 24 hours before FMT

12. RECORDING OF COMPLIANCE

Compliance will be assessed by checking the study medication (containers) returned at the follow-up visits and the final visit by the investigator.

All returned containers will be counted by the study coordinator and the number will be documented in the CRF.

13. ADVERSE EVENTS

• Definitions

Adverse events (AEs)

Adverse events (AEs) will be recorded at each regular scheduled study visit or study phone contact in the study patient record (source document) as well as on a specific AE form on the CRF.

An AE is any untoward medical occurrence in a study patient or clinical investigation subject administered a pharmaceutical product and which does not necessarily have a causal relationship with this treatment. An AE can therefore be any unfavourable and unintended sign (including an abnormal laboratory finding), symptom, or disease temporally associated with the use of a medicinal product, whether or not related to the medicinal product, e.g.:

- any new diagnosis
- any symptom that requires medical clarification or leads to in-patient admission (surgery or accident)
- any suspected adverse drug reaction (ADR)
- any symptom that appears on the study patient's medical records
- any event related in time with the application of the study medication and affecting the health of the study patient (including laboratory value changes)

Serious Adverse Events (SAE)

A serious adverse event (experience) is any untoward medical occurrence that at any dose:

- results in death
- is life-threatening
- requires inpatient hospitalization or prolongation of existing hospitalization
- results in persistent or significant disability/incapacity

Non-serious adverse events are all AEs that do not fall into any of the above categories.

Unexpected Adverse Drug Reactions

An unexpected adverse drug reaction (ADR) is an adverse reaction, the nature or severity of which is not consistent with the applicable product information.

Expected Adverse Drug Reactions

Fecal transplant has an excellent safety profile in patients with C. difficile colitis. Also FMT for C. difficile colitis seems to be safe in immunocompromised patients.^{64, 65}

In patients with IBD mild flu symptoms, abdominal pain and diarrhea after transplant have been observed.⁵¹ However, these are only transitory and no organ failure or organ toxicity has been reported.

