	The outcome will be determined by the modified pouchitis disease activity index (mPDAI) and the need for antibiotic therapy to control symptoms. The mPDAI is a composite index consisting of 2 disease variables (clinical criteria of pouchitis: number of bowel movements, blood in stool, urgency and fever with a maximum score of 6 and endoscopy criteria of pouch inflammation with a maximum score of 6. The maximum combined score is 12).	
	 Complete remission is defined as a mPDAI score = 0 and no need for antibiotics. Clinical remission is defined as a clinical mPDAI score ≤ 4 and no need for antibiotics. Symptomatic improvement is defined as a decrease from baseline in the mPDAI clinical subscore of 2 points and no need for antibiotics. Symptomatic worsening of the disease is defined by an increase in the mPDAI clinical subscore of 2 points or the need for antibiotics. 	
	The severity of the pouch inflammation will be evaluated by two pouchoscopies (week 0 and week 4). Endoscopic improvement is defined as a decrease from baseline in the mPDAI endoscopic subscore of 2 points.	
Primary variables	Safety and tolerability of endoscopically and orally applied FMT	
Secondary variables:	 Clinical remission (mPDAI score ≤4 points) and no need for antibiotic therapy at week 4. Clinical remission (clinical mPDAI score ≤ 4) and no need for antibiotics at week 8*. Clinical remission (clinical mPDAI score ≤ 4) and no need for antibiotics at week 16*. Endoscopic improvement of active pouchitis (decrease from baseline in mPDAI endoscopic subscore ≥ 2 points) at week 4. 	

	 Response: Symptomatic improvement of active pouchitis (decrease from baseline in mPDAI clinical subscore ≥ 2 points) and no need for antibiotic therapy at week 4. Response: Symptomatic improvement of active pouchitis (decrease from baseline in mPDAI clinical subscore ≥ 2 points) and no need for antibiotic therapy at week 8*. Response: Symptomatic improvement of active pouchitis (decrease from baseline in mPDAI clinical subscore ≥ 2 points) and no need for antibiotic therapy at week 8*. Response: Symptomatic improvement of active pouchitis (decrease from baseline in mPDAI clinical subscore ≥ 2 points) and no need for antibiotic therapy at week 16*. 	
	*Only patients who do not continue in open label extension	
	• Exploratory analyses (OL=Open label):	
	 Endoscopic improvement of active pouchitis (decrease from baseline in mPDAI endoscopic subscore ≥ 2 points) at in open label extension week 8. 	

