The rectal bleeding frequency will be calculated for the three evaluation days. The relative frequency for rectal bleeding will be calculated based on the total number of stools passed over the same three evaluation days ((total #stools with blood/total #stools)*100). The relative frequency will be evaluated against the following categories:

0% (none) < 20% (rare) > 20% (present daily)

Please note that the words, "none", "rare", and "present daily" in parentheses, correspond to the rectal bleeding categories on the mPDAI. These categories will be used to assign a mPDAI score for rectal bleeding.

Fecal urgency/abdominal cramping

The fecal urgency/abdominal cramping frequency will be calculated for the three evaluation days. The relative frequency for fecal urgency/abdominal cramping will be calculated based on the total number of stools for the same three evaluation days ((total #stools with cramping or urgency/total #stools)*100). The relative frequency will be evaluated against the following categories:

0% (none) < 50% (occasional) > 50% (frequent)

As with rectal bleeding, the words, "none", "occasional", and "frequent" in parentheses, correspond to the fecal urgency/abdominal cramping categories on the mPDAI. These categories will be used to assign a mPDAI score for fecal urgency/abdominal cramping.

Fever

If a subject indicates that they had a fever on none of the three evaluation days, the mPDAI score for "absent" will be recorded. If a subject indicates that they had a fever on one or more of the three evaluation days, the mPDAI score for "present" will be recorded.

20. STATISTICAL ANALYSIS

The following endpoints will be assessed

• Primary Endpoint:

Safety and Tolerability of FMT

- Number of study patients, who discontinued therapy
- Adverse events grouped by body system
- Changes in laboratory values
- Secondary Endpoints Clinical remission (mPDAI score <4 points and a decrease in the baseline mPDAI > 2 points) and no need for antibiotic therapy at week 4.
- Clinical remission (clinical mPDAI score ≤ 4) and no need for antibiotics at week 8*.
- Clinical remission (clinical mPDAI score ≤ 4) and no need for antibiotics at week 16*.
- Endoscopic improvement of active pouchitis (decrease from baseline in mPDAI endoscopic subscore ≥ 2 points) at week 4.

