The primary endpoint is the evaluation of safety and tolerability of FMT in patients with ADP. Secondary endpoints are endoscopic and clinical remission at week 4 in conjunction with no need for antibiotic therapy, clinical response and remission and no need for antibiotics at week 4,8 and 16, endoscopic improvement of pouchitis and quantitative changes of calprotectin after the initial FMT. All subjects with missing data for determination of endpoint status will be considered as a non-responder in the intention-to-treat analysis. For dichotomous outcomes we will compute the percentage of subjects having the event along with a 95% confidence interval. For continuous outcomes we will compute the mean and a 95% confidence interval for the mean as well as descriptive statistics such as median, range and upper and lower quartiles. In addition to computing these measures for all 20 subjects, we will compute them for subgroups of interest (e.g. endoscopic active vs inactive ADP). These estimates can then be used in the planning of a larger, hypothesis-based study.

• Sample size calculation

This trial is designed as a proof-of-concept study of FMT therapy, not a definitive evaluation of FMT therapy in patients with ADP. The goal is to evaluate the safety and feasibility of such a trial, as well as to estimate the effect sizes in placebo and FMT therapy groups in order to accurately estimate the sample size needed for subsequent evaluation in a larger definitive trial. Nonetheless, we estimated the minimum effect size this pilot study can detect. We assume a placebo remission rate (defined as clinical remission and no need for antibiotics) of 10%. The low placebo response rate is based on the inclusion criterion, which selects only patients needing continuous or recurrent antibiotic therapy in the setting of ADP. With a follow-up of 16 weeks with the requirement of clinical remission without antibiotic therapy at end of follow-up, a placebo response rate beyond 10% is highly unlikely. The recent case series of Stallmach et al. suggests an antibiotic-free remission rate of 80% and a response rate of 100% in the setting of repeated FMT.⁴⁹ With 20 patients (1:1 randomization), and a placebo response rate of 10%, we will have 80% power to detect an effect difference of 67.5%, that is, an antibiotic-free remission rate

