Distribute/Review Subject adverse events diary ^b			Х	X	X	X	Х

Study visits Chart for patients continuing in observation phase

Visit	6	7	8	9	Early termination ^g
Type of visit	Phone	Site	Site	Phone	Phone/site
Day	42	56	112	168	
	+/-3	+/-5	+/-7	+/-10	
Week	6	8	16	24	
mPDAI score	Х	X ^d	X ^d		Х
Concomitant Medication	Х	Х	X		Х
Adverse Events	Х	Х	X	X ^I	Х
Physical Exam		Х			Х
Blood Tests ^a		Х			Х
Stool sample		Xf	Xf		
Sigmoidoscopy (Pouchoscopy					
Distribute/Review Subject Diaries ^b	Х	Х			Х
Distribute/Review Subject adverse events diary ^b	Х	Xj			X

1.2 STUDY VISITS CHART OPEN LABEL EXTENSION FOR PATIENTS WITH RESPONSE ONLY OR NO RESPONSE OR EARLY TERMINATION DUE TO FLARE IN PLACEBO-CONTROLLED TRIAL SECTION

Visit	60L	70L	80L	90L	100L	110L	120L	130L	Early termination ^g
Type of visit	Site	Phone	Site	Site	Phone	Site	Site	Phone	Phone/site
Day (post 2nd transplant)	38 (0)	46 (8)	53 (15)	66 (28)	80 (42)	94 (56)	150 (112)	206 (168)	
38 (0)	38 (0)	+/-1	+3	+/-3	+/-3	+/-5	+/-7	+/-10	
Week (post 2nd transplant)	6 (0)	7 (1)	8 (2)	10 (4)	12 (6)	14 (8)	22 (16)	30 (24)	
mPDAI score		X ^d	X ^d	Х	Х	X ^d	X ^d		Х
Concomitant Medication	Х	Х	Х	Х	Х	Х	Х		Х
Adverse Events	Х	Х	Х	Х	Х	Х	Х	XI	Х
Physical Exam	Х			Х		Х			Х
Blood Tests				Х		Х			Х
Pregnacy test (urine)	Х								
Dispense FMT capsules + omeprazole	X ^g								
Stool sample			Xf	Xf		Xf	Xf		Х
Sigmoidoscopy (Pouchoscopy	Х			Х					
Endoscopic FMT	X ^h								
Distribute/Review Subject PDAI Diary ^b	Х	Х	Х	Х	Х	Х	Х		X
Distribute/Review Subject adverse events diary ^b	Х	Х	Х	Х	Х	Xj			X

^a Pouchoscopy visit 5 only in patients who are in remission (mPDAI<4) as assessed in visit 4 by phone or in patients with clinical active pouchitis, but not willing to participate in open label extension

^b There will be two subject diaries provided to the patient: One for the evaluation of the mPDAI will be provided at Screening. The study patient will complete this diary each day, beginning with the Screening visit, and ending with the Week 16 visit. Stool frequency, rectal bleeding, fecal urgency or abdominal cramps, and/or fever will be recorded. A minimum of three days of diary entries will be required during the week prior to randomization, Phone visit week 1 and 2 and Visit Week 4 and 8. The last three days of diary entries will be used to calculate stool frequency and fecal urgency/abdominal pain scores and clinical mPDAI subscores.

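### Under the visit 4 and visit 5 text, each arm's week-4 endoscopic improvement rate is capped by the share passing the clinical remission gate, so clinical status drives the arm difference; the documents conflict on who is scoped

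*Combined protocol and SAP*

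**What the plan says.** **Endpoint.** Sections 1, 5 and 20 list as a secondary endpoint "Endoscopic improvement of active pouchitis (decrease from baseline in mPDAI endoscopic subscore ≥ 2 points) at week 4". The response endpoints beside it also require that no antibiotic is needed. This one requires nothing beyond the fall in subscore, so it reads as a stand-alone mucosal outcome.

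**Who is scoped at week 4.** The documents give several answers:

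- Section 7 (phone visit 4) and Section 8 (visit 4) plan the pouchoscopy for patients in diary-based remission. Section 8, visit 5, states the restriction outright: "Pouchoscopy (in patients in clinical remission and no need for antibiotics only): Evaluation of endoscopic PDAI".
- Section 21, footnote a, covers remitters "or in patients with clinical active pouchitis, but not willing to participate in open label extension".
- Section 1 has no restriction: "The severity of the pouch inflammation will be evaluated by two pouchoscopies (week 0 and week 4").
- The Section 11 heading reads "Pouchoscopy (Screening, visit 5 or visit 6OL"), which treats the two visits as alternatives.
- Section 16 asks for an endoscopy at premature withdrawal, but only where possible. The early termination column of the placebo-controlled visits chart has no pouchoscopy.

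**Missing data.** Section 20, Clinical analyses: "All subjects with missing data for determination of endpoint status will be considered as a non-responder in the intention-to-treat analysis". No exception is made for measurements that the protocol does not schedule.

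**The concern.** Whether the endoscopic subscore exists at week 4 depends on an outcome that arises after randomization and that treatment is expected to change. Where it does not exist, the missing-data rule supplies a failure. If FMT improves symptoms, more FMT patients are scoped and fewer are failed automatically. An endoscopic difference then appears even if FMT does nothing to the mucosa.

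Sections 4 and 20 give effect-size estimation for a larger trial as a purpose of this study. An endoscopic rate built this way would carry the clinical effect into that planning under an endoscopic label.

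**Working it through.** **1. Inputs from the plan (Section 20, Sample size calculation).** 20 patients randomized 1:1, so 10 per arm; remission 10% on placebo and 77.5% on FMT; two-sided alpha 0.05; Fisher's exact test; stated power 80%.

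**2. The plan's own figure.** Summing binomial probabilities over all 11 × 11 outcomes for which Fisher's two-sided p is at most 0.05 gives 80.2%, which matches the stated 80%.

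**3. Does another visit supply a week-4 value?** Extension patients are next scoped at visit 6OL, after at least 10 days of antibiotics, so that subscore is not a week-4 value. The withdrawal endoscopy in Section 16 is conditional. Under the visit 4 and 5 text, nothing fills the gap.

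**4. Model.** Let r be the share passing the clinical gate, q the true chance of a fall of at least 2 endoscopic points, and d the share of non-passers who are scoped anyway. Set q equal in both arms and independent of symptoms, so the true endoscopic effect is zero. Then

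- reported rate in an arm = q × [r + d(1 − r)]
- reported difference = q × (1 − d) × (r on FMT − r on placebo)

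The documents give neither q nor d; both are assumptions.

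**5. Visit 5 text (d = 0), r = 77.5% and 10%.** The difference is q × 67.5 points.

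| q | FMT | Placebo | Difference | Fisher p ≤ 0.05 |
|---|---|---|---|---|
| 0.3 | 23.3% | 3.0% | 20 points | 4% |
| 0.5 | 38.8% | 5.0% | 34 points | 22% |
| 0.7 | 54.3% | 7.0% | 47 points | 45% |
| 1.0 | 77.5% | 10.0% | 67.5 points | 80% |

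With everyone scoped (d = 1) the difference is 0, and the rejection rate is at most about 1.3% over the q values tried.

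The levels are biased too. At q = 0.5 the true rate is 50% in both arms, but the rule reports 38.8% and 5.0%.

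**6. Sensitivity at q = 0.5.**

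- Some non-remitters scoped, as footnote a allows: d = 0.25 gives 0.5 × 0.75 × 67.5 = 25 points; d = 0.5 gives 0.5 × 0.5 × 67.5 = 17 points.
- More placebo patients pass the gate (d = 0): 30% gives 0.5 × (77.5 − 30) = 24 points; 40% gives 19 points; 50% gives 14 points.

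**7. How much is unobserved.** At the planning rates, 10 × 0.225 = 2.25 FMT patients and 10 × 0.90 = 9 placebo patients are unscoped. At q = 0.5 the FMT rate could lie anywhere from 38.75% to 38.75 + 22.5 = 61.25%, and the placebo rate from 5% to 5 + 90 = 95%. The difference is therefore bounded only by 38.75 − 95 = −56.25 and 61.25 − 5 = +56.25 points. The scored difference of 34 points is one value in that range, fixed by the scoring rule.

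**The case against.** Several objections stand and limit the point.

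- **The result does not repeat clinical remission.** A reader might infer that the endoscopic comparison is the remission comparison under another name. A scoped patient must still fall by at least 2 endoscopic points, so the two coincide only at q = 1. The difference could even vanish if improvement among scoped patients were 7.75 times as common on placebo (0.775/0.10).
- **It is not settled that only remitters are scoped.** That is the visit 4 and 5 text. Footnote a adds active patients who decline the extension, Section 1 sets no limit, and Section 16 adds a conditional withdrawal endoscopy.
- **The gate is not the remission endpoint.** Visit 4 uses the clinical subscore, which has a maximum of 6, and visit 5 calculates the score before pouchoscopy. The week-4 remission endpoint uses the mPDAI score, and Section 20 adds a required fall from baseline. A clinical cut-off of 4 out of 6 is lenient.
- **The 10% is argued from 16 weeks of follow-up.** More placebo patients may pass the gate at week 4; step 6 shows the effect.
- **True improvement may be low.** Baseline pouchoscopy follows at least 10 days of antibiotics stopped 24 hours earlier, and Section 20 expects endoscopically inactive patients, who may have no 2 points to lose. At q = 0.2 the spurious difference is 0.2 × 67.5 = 13.5 points and rejection is 0.9%.
- **No test is named for this endpoint.** Section 20 plans percentages with 95% confidence intervals, and Fisher's test appears only in the sample-size calculation for remission. A reader might take 22% or 45% as the plan's false-positive rate; the documents do not support that. At q = 0.5, rejection falls to 5.2% if 40% of placebo patients pass the gate, and to 4.2% if half of non-remitters are scoped.

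None of this removes the mechanism. While scoping follows clinical status and unscoped patients are failed, a clinical difference leaks into the endoscopic one.

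**Conclusion.** The point holds in this form: under the visit 4 and 5 text combined with the missing-data rule, each arm's week-4 endoscopic improvement rate cannot exceed the share passing the clinical gate, and the arm difference is driven by that share.

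In the no-effect illustration the bias is about 20 to 47 points for true improvement of 30% to 70%. At 50% true improvement it is 25 or 17 points with a quarter or half of non-remitters scoped, and 24 to 14 points with 30% to 50% of placebo patients passing the gate. These sizes assume improvement independent of symptoms and use the plan's 77.5% throughout; the base case also carries the 16-week 10% back to week 4.

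The harm is a biased effect estimate for planning the larger trial. The rejection rates are illustrative only. That readers would take the result as independent endoscopic support is a possibility, not something the documents state; the trial is a proof of concept with a safety primary endpoint. The conflict over who is scoped needs resolving whatever the size of the bias.

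**What to change.** No added procedure is needed.

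1. Name and define the endpoint as a composite: clinical remission without antibiotics and endoscopic improvement at week 4. Scoring a non-remitter as a failure is correct for that endpoint. Align it with the combined endoscopic and clinical remission endpoint that Section 20, Clinical analyses, already mentions, so that the two do not overlap undefined.
2. Do not apply missing = non-responder to a stand-alone endoscopic endpoint for patients whom the protocol does not scope. Report endoscopic change descriptively among those scoped, with the number scoped per arm, a statement that this subset is selected after randomization, and best-case and worst-case bounds for unscoped patients. At the planning rates only about one placebo patient would be scoped, so the bounds are essential.
3. Reconcile Section 1, Section 7 (phone visit 4), Section 8 (visits 4 and 5), the Section 11 heading, Section 16 and Section 21 footnote a on who is scoped at week 4.

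The cost is wording in those sections and in the endpoint lists of Sections 1, 5 and 20. The downside is that the trial gives up a stand-alone endoscopic claim, which data collected under the visit 5 text could not support.
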